3.7	Timing of final analysis i.e. all outcomes analysed collectively or analyses performed according to planned follow-ups	The primary outcome and the key secondary outcome are analysed collectively.
-----	--	--

Section 4: Statistical principles and protocol deviations

4.1	Confidence intervals and P-values Specification of level of statistical significance and confidence intervals to be reported. Describe, if relevant, rationale for adjustment for multiple testing and how type 1 error will be controlled for	For the primary outcome, a one-sided test at $\alpha = 0.025$ will be used. Non-inferiority will be concluded if the upper bound of the 95% confidence interval is equal to or below the margin of 0.13 mm. Secondary outcomes will be tested two-sided at $\alpha = 0.05$, with corresponding 95% confidence intervals. No adjustment for multiple testing will be made; secondary results are considered exploratory.

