4.2	Adherence/compliance and protocol deviations Define adherence/compliance and how this is assessed in the study. Define protocol deviations and which protocol deviations will be summarized and presented	Main challenges: - Treatment adherence : Degree of adherence is assessed by patient-reported days without OKL or hours without DIMS between visits as "No-wear". "No-wear" is included in the mixed effects model as a time-varying post-randomisation variable (see 6.2) and in a sensitivity analysis (see 6.3). Missing measurements is assumed to be best case = 0 days/hours without OKL/DIMS. Day time hours is assumed to be 16 hours. Following defines the binary definitions of adherence: -- Low adherence (in the 6-month period between visits) 
 OKL: > or = 75% of days without OKL DIMS: > or = 75% of hours without DIMS -- Moderate Adherence (in a 6-month period) 
 OKL: 25-75% of days without OKL DIMS: 25-75% of daytime hours without DIMS -- High Adherence (in a 6-month period) 
 OKL: < or = 25% of days without OKL DIMS: < or = 25% of daytime hours without DIMS OKL: Each eye contributes with 50% of adherence; E.g. The right eye has 25% of days without OKL and the left eye has 75% of days without OKL, which gives a total % days without OKL of: $(0.25/2) + (0.75/2) = 50\%$, corresponding to moderate adherence. - Technical error in the reading of the autorefractor apparatus output at baseline resulting in four children included without correct cycloplegic refraction, assuming random error. The true output was available for analysis. No children were excluded by this error. This is handled by making a sensitivity analysis (see 6.3) - Drop out at treatment allocation/follow-up , will be handled by offering the participant a follow-up examination corresponding to the 18-month visit (noting use of types of treatments used and days using treatment) and used in a sensitivity analysis (see 6.3).

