		
 - Ocular magnification correction algorithm of the choroid thickness for the key secondary outcome: -- Missing corneal radius is handled as 0 (= no correction for corneal radius). It is noted in which participants and visits this occur, to report how many measurements this will concern. -- Missing refractive error is handled as 0 (= no correction for refractive error). It is noted in which participants and visits this occur, to report how many measurements this will concern. -- Algorithm non-functioning in participants with a refractive error = 0 (e.g. the OKL group) and an axial length exceeding maximum to be handled in the algorithm. It is handled by calculating the theoretical refractive error for the relevant visit using the AL increase since baseline: -0.25D is added to the baseline cycloplegic refractive error for every 0.15 mm longer AL for males and every 0.13 mm longer AL for females (Jakobsen, Gehr & Moller 2020). It is noted in which participants and visits this occur, to report how many measurements this will concern.
4.3	Analysis populations Define analysis population i.e. intention-to-treat, per-protocol, complete case, safety population	
As adherence challenges are expected (see 4.2) both Intention to treat and a per-protocol approach will be performed.
 
The primary analysis will follow the intention-to-treat (ITT) principle, including all randomized participants regardless of adherence or protocol deviations.
 
A per-protocol (PP) analysis will be conducted as a sensitivity analysis, including participants with high or moderate adherence and no major protocol violations described in (4.2)
 
Missing data will be handled using mixed effects models under the missing at random (MAR) assumption (6.4). Additional sensitivity analyses will be performed to assess the impact of deviations

Section 5: Study population

5.1	Screening (if applicable) Describe screening data to determine eligibility (i.e. scoring and scales)	
Potential participants were preliminary referred from private ophthalmic practices to the Department of Ophthalmology, University Hospital of Southern Denmark, Lillebaelt Hospital, Vejle, Denmark, based on cycloplegic refractive error in relation to age. After screening, potential eligible participants and their guardians were invited to an information meeting.

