6.2	
Primary analysis methods
 
Describe in details which statistical methods will be used (i.e. regression), how treatment effects will be presented (i.e. which effect measure - OR, HR etc.) and if estimates will be adjusted for covariates (see appendix). If analyses will be adjusted for covariates, describe how the sufficient adjustment set will be defined (i.e. using DAGs)
 
Describe methods used to check assumptions (i.e. normality, proportional hazards) behind the statistical models, and alternative methods if assumptions about distribution do not hold.
	
Primary outcome
 
Blinded interpretation of primary analysis: Study groups labelled as A & B is presented to the authors.
 
We will compare the two treatment groups with one linear mixed effects regression model with the participant as random intercept using axial length as the dependent variable and visit as the (categorical) independent variable, with baseline as reference point. Both eyes are used in the analysis.
 
Both an Intention to treat and a per-protocol approach will be performed.
 
The regression models will be reported as unadjusted, and as adjusted for the following covariates for a more precise result:
 
 - Age at baseline - Cycloplegic spherical equivalent refractive error at baseline - Axial length at baseline - Number of myopic parents (spherical equivalent refractive error $\leq -0.50D$) at baseline 
The adjusted model will also be adjusted for time-varying post-randomisation variable to explain the performance bias in the “effect” of adherence:
 
 - Non-wear (patient-reported as the participants total amount of days without OKL or hours without DIMS) 
The non-inferiority margin is 0.13 mm. Non-inferiority will be concluded if the upper bound of the 95% confidence interval for the estimated treatment difference (DIMS – OKL) after 18 months is equal to or below 0.13 mm, in both ITT and PP analyses.
 
Results will be presented as estimated coefficients with standard errors (SE), p-values (p) and 95% confidence intervals (CI):
 
 1) Mean axial elongation at each 6-month interval over 18 months by treatment group 2) Between-group differences in axial elongation at each time point. 
Model assumptions will be assessed using Q-Q plots for normality of residuals and random effects, and residual vs. fitted plots to check for homoscedasticity. If assumptions are violated (e.g. non-normality or heteroscedasticity), robust standard errors or non-parametric bootstrapping will be applied.
 
Key secondary outcome: A similar approach will be made for the key secondary outcome.

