6.3	Additional analysis methods	In case of non-inferiority, superiority is tested in the same population at 0.05 without a statistical penalty because of the

	
Describe any planned sensitivity and subgroup analysis including how subgroups will be defined (see appendix).
	
closed testing principle. Superiority is declared if the upper 95%CI bound is below zero (Figure 3).
 
In case of inferiority, a subgroup analysis of participants in the DIMS group with axial elongation exceeding emmetropic progression rate will be conducted as a hypothesis generating post hoc analysis.
 
Adherence: Sensitivity analysis of binary adherence “No-wear”, is repeated in groups of “high adherence”, “moderate adherence” and “low adherence” (see 4.2).
 
Protocol deviations: -Sensitivity analysis with and without the four children mistakenly included by technical error in the autorefractor apparatus result reading at baseline (see 4.2). Analysis is either provided in supplementary or by request.
 
-Sensitivity analysis of dropouts.
 
Additionally, post hoc analysis: - axial elongation after 18 months in relation to age at enrolment. - axial elongation after 18 months in relation cycloplegic spherical equivalent refractive error at baseline.

6.4	
Missing data Describe how missing data will be explored and which assumptions and methods will be used to handle missing data (i.e. multiple imputation)
	Missing data assumed to be missing at random (MAR) and will be handled by the mixed effects regression model.

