6.2 Primary analyses table template

Table 3: Linear mixed-effects models of axial length for the x participants

Visit	The DIMS group Difference from baseline mm (95% CI) SE, p	The OKL group Difference from baseline mm (95% CI) SE, p	The Difference between DIMS and OKL (DIMS – OKL) mm (95% CI) SE, p	Missing
Unadjusted				
Baseline	(Reference)	(Reference)	(Reference)	xx (xx%)
6 Months	–x (–x to x) x, x	–x (–x to x) x, x	–x (–x to x) x, x	xx (xx%)
12 Months	–x (–x to x) x, x	–x (–x to x) x, x	–x (–x to x) x, x	xx (xx%)
18 Months	–x (–x to x) x, x	–x (–x to x) x, x	–x (–x to x) x, x	xx (xx%)
Adjusted				
Baseline	(Reference)	(Reference)	(Reference)	xx (xx%)
6 Months	–x (–x to x) x, x	–x (–x to x) x, x	–x (–x to x) x, x	xx (xx%)
12 Months	–x (–x to x) x, x	–x (–x to x) x, x	–x (–x to x) x, x	xx (xx%)
18 Months	–x (–x to x) x, x	–x (–x to x) x, x	–x (–x to x) x, x	xx (xx%)

[figure not shown]
Linear mixed-effects model with the participant as a random intercept, axial length as the dependent variable, visit as the independent variable, and baseline as the reference visit. DIMS = Defocus Incorporated Multiple Segment spectacle lenses; OKL = Orthokeratology lenses; mm = millimetre; 95%CI = confidence interval; SE = standard error; p = p-value

Figure 2: Model-adjusted mean and 95% Confidence interval of axial length from baseline to 18 months

DIMS = Defocus Incorporated Multiple Segment spectacle lenses; OKL = Orthokeratology lenses; mm = millimetre

Figure 3: 2-sided 95% Confidence interval error bars and noninferiority margin for the difference in axial elongation between DIMS spectacle lenses and OKL after 18 months (Possible scenarios illustrated and adapted from (Piaggio et al. 2010)). The graphic will show the results of the Intention to Treat and the per-protocol model, both with and without adjustments.

DIMS = Defocus Incorporated Multiple Segment spectacle lenses; OKL = Orthokeratology lenses; Δ = noninferiority margin

[figure not shown]
Key secondary outcome:

Table 5: Linear mixed-effects models of overall eye length for the x participants

Visit	The DIMS group Difference from baseline mm (95% CI) SE, p	The OKL group Difference from baseline mm (95% CI) SE, p	The Difference between DIMS and OKL (DIMS – OKL) mm (95% CI) SE, p	Missing
Unadjusted				
Baseline	(Reference)	(Reference)	(Reference)	xx (xx%)
6 Months	–x (–x to x) x, x	–x (–x to x) x, x	–x (–x to x) x, x	xx (xx%)
12 Months	–x (–x to x) x, x	–x (–x to x) x, x	–x (–x to x) x, x	xx (xx%)

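### Section 6.2 requires per-protocol success for non-inferiority, section 4.3 calls per-protocol a sensitivity analysis, and section 4.2 admits children with unknown wear to that set as fully adherent

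*SAP*

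**What the plan says.** **Decision rule.** Section 6.2 sets the condition that the upper 95% bound for DIMS minus OKL at 18 months "is equal to or below 0.13 mm, in both ITT and PP analyses". Section 4.3 assigns different roles to the two sets: "The primary analysis will follow the intention-to-treat (ITT) principle", and "A per-protocol (PP) analysis will be conducted as a sensitivity analysis". Section 4.1 gives the criterion without naming a set: "Non-inferiority will be concluded if the upper bound of the 95% confidence interval is equal to or below the margin of 0.13 mm". Section 6.3 adds a further step: "In case of non-inferiority, superiority is tested in the same population at 0.05". The Figure 3 template displays both sets and does not say which decides: "The graphic will show the results of the Intention to Treat and the per-protocol model, both with and without adjustments".

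**PP membership.** Section 4.3 defines PP as "including participants with high or moderate adherence and no major protocol violations described in (4.2". Section 4.2 classifies each six-month period by reported non-wear: up to 25% is high adherence, 25% to 75% moderate, and 75% or more low. For absent reports the rule is "Missing measurements is assumed to be best case = 0 days/hours without OKL/DIMS". Section 4.3 makes no exception to this rule for PP.

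**The concern.** A sensitivity analysis informs the reading of a result; a required condition decides it. Section 4.3 gives PP the first role and section 6.2 the second. Someone working from 4.3 and 4.1 could report non-inferiority on ITT when PP has failed, which 6.2 does not allow. The unclear status carries into 6.3, where superiority is tested in the same population although 6.2 uses two.

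Once PP can block the conclusion, who belongs to it is part of the decision rule. In a non-inferiority comparison, PP is there to check whether unworn time makes the two arms look alike under ITT. A rule that counts unknown wear as full wear weakens that check, because a child who did not wear the treatment and did not report it stays in the set.

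**Working it through.** **1. The SAP's own figure.** Inputs from section 3.3: margin 0.13 mm, SD 0.18 mm, one-sided alpha 0.025, power 80%, with no true difference assumed. n = 2 × [0.18 × (1.960 + 0.842) / 0.13]² = 30.1, so 31 per group by the normal approximation. The t-based calculation gives power 0.799 at 31 and 0.812 at 32, so the stated 32 per group is reproduced.

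**2. What the missing-wear rule does.** Non-wear cannot be below 0, so coding a missing value as 0 gives the lowest possible value. Under any sensible way of combining periods, the child's class can only stay the same or move towards higher adherence.

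Example: a child truly has 80% non-wear in all three periods, which is low adherence and outside PP. Suppose periods are averaged; this is an assumption, since the SAP does not say how they combine.

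- One report missing: (80 + 80 + 0)/3 = 53%, moderate, in PP.
- Two missing: (80 + 0 + 0)/3 = 27%, moderate, in PP.
- Three missing: 0%, high, in PP.

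**3. How often the status of PP would matter.** Let d be the true difference, taken as equal in both sets, with PP nested in ITT.

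- SE(n) = 0.18 × √(2/n)
- Probability that a set passes = Φ((0.13 − d)/SE(n) − 1.96)
- Joint probability from a bivariate normal with correlation √(n_PP/n_ITT)

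ITT size: section 3.3 gives 90 children in 1:1 allocation and 20% observed dropout, so 45 × 0.8 = 36 per group. This stands in for the number informing the 18-month comparison. SE(36) = 0.0424, and at d = 0 the pass probability is Φ(0.13/0.0424 − 1.96) = Φ(1.10) = 86.5%. The SAP gives no PP size, so a range is shown.

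| PP per group (ITT 36) | ITT passes, PP fails, d = 0 | Same, d = 0.03 mm |
|---|---|---|
| 35 | 2.0% | 3.1% |
| 34 | 3.3% | 4.9% |
| 32 | 5.7% | 8.1% |
| 27 | 12.6% | 15.6% |

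The last row uses 45 × 0.6 = 27, which borrows the SAP's 40% dropout allowance as a PP size. It is an unfavourable case. PP excludes for adherence only at 75% or more non-wear, and best-case coding keeps non-reporters in, so the upper rows fit the SAP's definition better.

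**4. Error rate at the margin.** At d = 0.13 mm the ITT-only rule passes 2.5% of the time. The joint rule, by the same formula with 36 in ITT, passes 1.7% with 32 in PP and 1.3% with 27. Neither reading exceeds the stated 0.025.

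**The case against.** The strongest reply on the decision rule is that 6.2 already settles it. It is the only place that ties the conclusion to named sets. Section 4.1 is compatible with it, and 4.3 never says that ITT alone suffices. This stands. A reader might infer that the SAP licenses two contradictory conclusions when ITT passes and PP fails. The text does not go that far: the defect is a label in 4.3 and an unnamed set in 4.1 that do not match the rule in 6.2. Likewise, the same population in 6.3 can be read as the sets used for non-inferiority, so it is a follow-on ambiguity and not a separate contradiction.

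On membership, the reply is that the coding was pre-specified and may touch few children. Section 3.6 has non-wear since the last visit recorded at every visit, so the rule matters mainly for visits attended without a report. The Table 2 template has a column for missing data, though not by arm. Dropouts are offered an examination that records treatment use, and a sensitivity analysis of dropouts is planned. All of this limits the likely size. It does not change the fact that unknown wear is classified as full wear in a set that can decide the trial, and none of the planned analyses varies that coding.

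Two further inferences should be resisted. The first is that the coding biases the trial towards non-inferiority: direction and size depend on missing wear by arm, which the SAP does not give. The second concerns the OKL rule that each eye contributes half, which might suggest that one missing eye report could never yield low adherence. The SAP does not describe one-eye missing reports or apply the best-case rule to them.

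**Conclusion.** The point holds as a should-fix. PP is a required condition in 6.2 and a sensitivity analysis in 4.3, with 4.1 silent on the set; 6.2 should govern. The coding of missing non-wear as 0 is wrong for PP membership because it places children of unknown adherence in the highest class.

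The text conflict is certain; its size is not. With 36 ITT children per group and 35 to 32 in PP, the status of PP changes the answer in about 2% to 6% of trials at no true difference and 3% to 8% at 0.03 mm, rising to 13% and 16% with 27 in PP. These figures assume SD 0.18 mm, PP nested in ITT, and the same true difference in both sets. They also use a simple two-group comparison in place of the mixed model, in which ITT includes all randomised children. They measure the decision-rule conflict only. The effect of the missing-wear coding cannot be quantified from the SAP, and no bias or inflated error rate is claimed. How the three periods combine, and which deviations in 4.2 count as major, are mainly missing detail, best settled in the same edit.

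**What to change.** Issue a dated SAP revision before the A/B labels are revealed:

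1. In 4.1 and 4.3, state that non-inferiority requires both ITT and PP, as in 6.2. In 6.3, name the set used for the superiority test.
2. For PP membership and the adherence groups in 6.3, do not set missing non-wear to 0. Leave it missing and use recorded treatment-use or discontinuation data where available. Treat a child whose adherence cannot be established as not evaluable for PP. Report best-case coding as a sensitivity analysis, with counts of missing wear by arm.
3. In the same edit, state how the three six-month periods combine into one PP decision and which deviations in 4.2 are major.

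**Cost.** No new data are needed. The trial is open label and the SAP is already approved, so the reason for the change should be recorded. Treatment-use data will exist only for dropouts who accepted the offered examination. The PP set may shrink somewhat and its interval widen: by the formula above, power at no true difference is 82% with 32 per group, 76% with 27 and 72% with 25. With 36 in ITT, requiring both sets gives about 81% with 32 in PP and 74% with 27. Excluding unclassifiable children may introduce selection, which the best-case analysis helps to assess.

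This revision does not settle whether the adjusted or the unadjusted model decides, or how missing non-wear is handled as a covariate in the adjusted model. Both need their own statement.

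### Averaging OKL non-wear over the two eyes lets a low-adherence eye stay in the per-protocol set when its fellow eye is worn enough, which mainly weakens that set as a check on non-inferiority

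*SAP*

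**What the plan says.** Section 4.2 sets three OKL classes per 6-month period. Low is "OKL: > or = 75% of days without OKL", moderate is "OKL: 25-75% of days without OKL", and high is 25% or less. It then averages: "OKL: Each eye contributes with 50% of adherence". Its illustration is a child for whom "The right eye has 25% of days without OKL and the left eye has 75% of days without OKL". The total is 50%, "corresponding to moderate adherence". Missing non-wear is filled in favourably: "Missing measurements is assumed to be best case = 0 days/hours without OKL/DIMS".

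Section 4.3 defines the PP set by participant, "including participants with high or moderate adherence and no major protocol violations described in (4.2"). It has no exclusion by eye, and 4.2 does not name one-eyed non-wear as a violation.

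Section 6.2 fits axial length with a random intercept for participant and states: "Both eyes are used in the analysis". Its non-wear covariate is the participant's total and enters only the adjusted model. Non-inferiority is concluded only if the upper 95% bound of DIMS − OKL is at or below 0.13 mm in both the ITT and the PP analysis.

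**The concern.** The outcome is analysed by eye, and an orthokeratology lens acts only on the eye that wears it. Membership of the PP set, however, is decided on an average over two eyes. A well-worn fellow eye can therefore carry a poorly worn or unworn eye into the set as an OKL-treated eye. The averaging rule is written for OKL only. Spectacles are on or off for both eyes together, so DIMS has no counterpart.

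The PP analysis matters here because 6.2 makes it one of two analyses that must pass. ITT contains poorly exposed eyes by design, and PP is the check on whether diluted exposure produced the result. By 2.1, OKL slows axial growth. Under-treated OKL eyes are thus expected to raise mean OKL elongation, lower DIMS − OKL and lower its upper bound. If PP keeps them, the check is weaker than it appears.

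**Working it through.** **The plan's own figure.** (25% + 75%)/2 = 50%, moderate. This reproduces 4.2.

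**Which eyes are kept.** Let a and b be the two eyes' non-wear. The child is clearly below the low class when (a + b)/2 < 75%, that is, b < 150% − a.

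| Eye a | Fellow eye b | Child average | Class |
|---|---|---|---|
| 80% | 25% | 52.5% | moderate, both eyes in PP |
| 100% | 0% | 50% | moderate, both eyes in PP |
| 100% | 25% | 62.5% | moderate, both eyes in PP |
| 100% | 49% | 74.5% | moderate, both eyes in PP |
| 100% | 50% | 75% | boundary: in both the low and the moderate range |

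A never-treated eye stays whenever its fellow eye is below 50%, and an 80% eye whenever its fellow eye is below 70%. If missing non-wear is set to 0 eye by eye, retention becomes easier still.

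**Size, under assumptions.** Let f be the share of OKL children in the PP set with one eye essentially unworn, and E the extra 18-month growth of that eye over an OKL-treated eye. The SAP gives neither. Each such child contributes one affected eye of two, so the shift in DIMS − OKL is −f × ½ × E.

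- Low: 0.05 × 0.5 × 0.2 = 0.005 mm; 0.005/0.13 = 4% of the margin.
- High: 0.10 × 0.5 × 0.4 = 0.020 mm; 0.020/0.13 = 15% of the margin.

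**Effect on the PP test alone.** Section 3.3 gives SD 0.18 mm and 32 children per group before dropout. Taking one value per child, SE = 0.18 × √(2/32) = 0.045 mm. When the true difference equals the margin, the one-sided error is Φ(−1.96 + shift/SE):

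- shift 0.005 mm: Φ(−1.85) = 0.032;
- shift 0.020 mm: Φ(−1.52) = 0.065.

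The nominal level is 0.025. With 45 per group (90 children, 1:1) the SE is 0.038 mm and the figures are 0.034 and 0.076. These are not error rates for the trial's conclusion, which also needs ITT to pass.

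**Why an excluded eye must leave at every visit.** The model uses absolute axial length with an intercept for the child only. If an eye's baseline stays but its follow-up goes, the length difference between the eyes enters the estimated change. Section 5.1 allows 1.50 D of anisometropia. At 0.13 mm per 0.25 D (3.3, a conversion for change over time, used here only as a rough guide) that is 6 × 0.13 = 0.78 mm between eyes. The child's two-eye mean could then move by 0.39 mm.

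**The case against.** Several counter-arguments carry weight.

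- **The moderate band dilutes as well.** If growth is linear in wear, a 0%/100% child and a 50%/50% child both add E/2 to the child's mean. The plan keeps the second deliberately, and an eye-level rule would keep it too. This stands: averaging is not the only source of dilution, nor necessarily the main one. But the SAP neither states nor justifies linearity, and it treats 75% or more as too little exposure for the PP set.
- **The direction is not fixed.** Eyes at 100% and 50% average 75%. If that is read as low, an eye with only 50% non-wear leaves as well, which works against non-inferiority. DIMS children with 25–75% non-wear also stay in the PP set, and their dilution raises DIMS − OKL. A reader might infer an error that always favours the claim; the document does not support that.
- **The illustration is not a clean case.** A reader might take the 75% eye in 4.2 as proof that an eye in the low class is kept. Exactly 75% falls in both classes, and the cut-offs are written for the child. The 80%/25% pair shows the point without that ambiguity.
- **Section 6.3 helps.** It repeats the analysis by adherence class. In the high class the average is at most 25%, so neither eye can exceed 50% recorded non-wear. That gives a useful cross-check, but it is not part of the decision rule in 6.2.
- **Such children may be few.** At 10%, 4 or 5 of 45 OKL children would each need one eye essentially unworn. The only sign of one-eyed non-wear in the SAP is an illustration. This limits the likely size, not the logic.
- **A child-level rule is defensible.** Children were randomised and the rule is pre-specified. That argues for offering a worse-eye version, which keeps the child as the unit.

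**Conclusion.** The point holds in a limited form. The averaging rule in 4.2, the participant-level PP set in 4.3 and the two-eye analysis in 6.2 together allow an OKL eye with more than 75% non-wear to remain in an analysis that must pass, provided its fellow eye is worn enough. The main effect is to lower DIMS − OKL and so to weaken PP as a check on non-inferiority.

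It would go too far to say that every low-adherence or untreated OKL eye stays, since retention depends on the fellow eye. It would also go too far to call the bias known or large. The range of 0.005–0.020 mm (4–15% of the margin) rests wholly on the assumed 5–10% of OKL children and 0.2–0.4 mm of extra growth, and it is smaller if one-eyed non-wear is rarer. The rule should be changed, but the point does not by itself invalidate the planned conclusion.

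**What to change.** In 4.2 and 4.3, base PP membership in the OKL arm on each eye's own recorded non-wear. Remove an excluded eye at all visits including baseline, or add an eye-within-child random intercept. Keep the fellow eye if it qualifies, and use the child average for Table 2 only. If exclusion by eye is not wanted, class the child by the worse eye.

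The revised text should also say which class exactly 75% belongs to, and how the three 6-month classes combine into one PP decision. The SAP gives no such combining rule, and one is needed under either approach.

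Section 1.8 dates the analysis to December 2025. If it has already been run, report this PP result beside the planned one and label it as added.

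The cost is wording and recoding, provided non-wear was recorded by eye. The illustration in 4.2 implies that it was, but 3.6 and 6.2 describe a participant total, so this should be confirmed. The downsides are slightly fewer OKL eyes or children in the PP set and, with the eye-level version, an exclusion rule that works by eye in OKL but by child in DIMS.

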5.1	Eligibility Summarize in- and exclusion criteria	
Inclusion criteria:
 
 - Myopic children aged 6 to 12 years: Myopia of the 6 to 8-year-olds (inclusive): -1.00 to -4.75 D spherical component and up to -2.50 D of regular astigmatism (both eyes). Myopia of the 9 to 12-year-olds (inclusive): -2.00 to -4.75 D spherical component and up to -2.50 D of regular astigmatism (both eyes). - Anisometropia \leq 1.50 D cycloplegic spherical equivalent refractive error. - Best corrected visual acuity at age 6 to 12 years (inclusive): 0.8 Snellen (equivalent to \geq 3/5 letter on the 0.8 line = 78 ETDRS letters) 
Exclusion criteria:

	
 - Manifest or intermittent squint. - Contraindications to the use of OKL comprising (not exhaustive): keratoconus, chronic allergic conjunctivitis and keratoconjunctivitis sicca. - Previous eye surgery. - Chronic eye disease demanding daily use of eye drops. - Non-compliance to eye examinations (unstable fixation or anxiety towards contact lenses). - Previous myopia control treatment. 
After trial commencement, project staff confused criteria of best corrected visual acuity in the 9 to-12 years group with the criteria of the 6 to 8-years group resulting in four children of 9 years old included using the 6 to 8-years old criteria for best corrected visual acuity. No children were excluded by this mistake. Preliminary referral or screening was not based on the visual acuity criteria. The visual acuity criterium was chosen to screen for abnormal vision. After clinical considerations, the visual acuity inclusion criteria in the 9–12-year group was too strict, as some of the younger children may not have fully matured visual development as 9-year-olds. Hence the inclusion criteria was adjusted to age 6 to 12 years (inclusive): 0.8 Snellen (equivalent to $\geq 3/5$ letter on the 0.8 line = 78 ETDRS letters), which reflects the visual acuity criteria used in the CONTROL-study (Jakobsen & Møller 2021)

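### A missing refractive error is entered as 0 D in the choroid magnification correction, a value outside the eligible range for baseline and DIMS eyes, and no sensitivity analysis is named for it

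*SAP*

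**What the plan says.** SAP 6.1 defines overall eye length as axial length (AL) plus subfoveal choroidal thickness (SFCT). It corrects choroidal thickness for ocular magnification with an algorithm that takes axial length, mean corneal radius and refractive error.

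SAP 4.2 gives three rules for problem inputs:

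- Refractive error: "Missing refractive error is handled as 0 (= no correction for refractive error".
- Corneal radius: "Missing corneal radius is handled as 0 (= no correction for corneal radius".
- A failure case: "Algorithm non-functioning in participants with a refractive error = 0 (e.g. the OKL group) and an axial length exceeding maximum". Here the plan computes a theoretical refraction. It takes the baseline cycloplegic refraction and makes it 0.25 D more myopic for each 0.15 mm of axial growth in males or 0.13 mm in females.

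Each rule carries the same undertaking: "It is noted in which participants and visits this occur, to report how many measurements this will concern".

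SAP 5.1 (Eligibility) admits both eyes at -1.00 to -4.75 D sphere (6 to 8 years) or -2.00 to -4.75 D (9 to 12 years), with up to -2.50 D of astigmatism. SAP 4.1 calls secondary results exploratory. SAP 4.3 and 6.4 leave missing data to the mixed model under missing at random (MAR).

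**The concern.** The change in overall eye length differs from the change in axial length, the primary outcome, only through the change in choroidal thickness. An artefact in the choroid correction therefore falls on the one component that the key secondary outcome adds.

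The plan glosses 0 as no correction, but in a trial of myopic children 0 D is not neutral. If refraction is missing at one visit and present at another, the same eye is corrected differently at the two visits, and the difference appears as choroidal change. The arms are not affected alike. The OKL lens reduces central corneal power (SAP 3.1), and SAP 4.2 itself gives the OKL group as its example of a refractive error of 0, whereas a DIMS eye stays myopic.

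The plan also treats one quantity in two ways. A missing refraction becomes 0 below the algorithm's axial length limit but, on a natural reading, becomes the theoretical value above it.

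**Working it through.** No sample size, power or alpha figure in the SAP depends on this rule, so there is no stated figure to reproduce. The check compares the imputed 0 with what the plan's own conversion would give.

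**1. Size of the input error**

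Theoretical refraction = baseline refraction - 0.25 × (AL growth / k), with k = 0.15 mm (males) or 0.13 mm (females), from SAP 4.2. The largest eligible spherical equivalent is -4.75 - 2.50/2 = -6.00 D. The growth values are assumed.

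| Baseline (D) | AL growth (mm) | Male (D) | Female (D) |
|---|---|---|---|
| -1.00 | 0 | -1.00 | -1.00 |
| -2.00 | 0.30 | -2.50 | -2.58 |
| -4.75 | 0.30 | -5.25 | -5.33 |
| -6.00 | 0.50 | -6.83 | -6.96 |

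Example: -2.00 - 0.25 × 0.30/0.13 = -2.58 D. Entering 0 is thus wrong by at least 1.00 D, and by about 7 D at the extreme, for an eligible eye that is pre-treatment or on DIMS. For an OKL eye on treatment this comparison does not apply, because the cornea has been flattened.

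**2. Route to the outcome**

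Change in overall eye length = change in AL + change in SFCT. If the input is wrong at one visit only, the resulting error in SFCT passes in full into the change. If it is wrong in the same way at every visit of an eye, most of it cancels. The rule does harm when refraction is missing at some visits and measured at others.

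**3. Possible size in mm**

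The following are assumptions, not document figures: SFCT 200 to 400 µm; effect on thickness 0.2% to 2% per dioptre; 5% to 20% of measurements affected. Input error is 1 to 6 D.

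- Per affected measurement, low end: 200 × 0.002 × 1 = 0.4 µm = 0.0004 mm.
- Per affected measurement, high end: 400 × 0.02 × 6 = 48 µm = 0.048 mm.
- Group-mean shift: 0.0004 × 0.05 = 0.00002 mm to 0.048 × 0.20 = 0.0096 mm.

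For scale, the planning values for axial length (SD 0.18 mm, 32 per group, SAP 3.3) give a standard error of the group difference of 0.18 × √(2/32) = 0.045 mm. If overall eye length has a similar SD, the upper shift is 0.0096/0.045 = 0.21 of a standard error, and the lower is negligible.

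**4. Mitigation in the plan**

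SAP 4.2 counts the affected measurements. SAP 4.3 promises sensitivity analyses of deviations in general terms. SAP 6.3 names analyses for adherence, for the four children with a misread autorefractor result and for dropouts, but none for substituted inputs. A count does not show how far the estimate moves.

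**The case against.** The strongest reply is that little is at stake. The primary outcome does not use the algorithm, secondary results are exploratory, and substituted measurements are logged and reported. Refraction decides eligibility, and SAP 4.2 says the true output was available for the four misread children, so a baseline refraction may seldom be missing. All of this stands and limits the weight of the point. It does not make 0 D a sensible value where refraction is missing in a baseline or DIMS eye.

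Four stronger readings are tempting, and the SAP does not support them:

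- *The missing-value rule makes the algorithm fail.* The stated failure needs a refractive error of 0 together with an axial length above the algorithm's maximum. The plan already gives a remedy for that case, which appears to cover an imputed 0 as well. No failure at 0 alone is reported.
- *The plan has a better substitute for both inputs.* It has one for refractive error only. For corneal radius it offers none. A radius of 0 is impossible in any eye, so it reads as a code for not entered. What remains is that a radius used at some visits and not at others can make the correction inconsistent within an eye.
- *0 D is wrong for every child.* It may be near the measured value in an OKL eye on treatment. Entering the theoretical refraction there could create the inconsistency complained of: a myopic value at the missing visit beside measured values near 0 at the others. The four misread children are also a caveat to the 1.00 D minimum, since the SAP does not give their true refraction.
- *The key secondary comparison is shown to be biased.* Bias is possible, but neither its direction nor its size follows from the documents.

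**Conclusion.** The point holds for refractive error in baseline and DIMS eyes. The plan enters a value outside the eligible range although it already defines a computable alternative, and the resulting error can differ by arm. The input error is 1.00 D to about 7 D, the upper end resting on an assumed 0.50 mm of growth. The effect on overall eye length cannot be fixed from the SAP. Under the stated assumptions the group-mean shift is at most about 0.01 mm and could be negligible.

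For corneal radius the supportable point is narrower: the correction should be consistent across the visits of one eye. This is a worthwhile, inexpensive correction to an exploratory key secondary analysis. It has no bearing on the non-inferiority conclusion for axial length.

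**What to change.** In SAP 4.2, replace the two rules that substitute 0:

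1. **Missing refractive error, pre-treatment visits (either arm):** use the measured baseline cycloplegic refraction.
2. **Missing refractive error, DIMS follow-up visits:** use the theoretical refraction already defined in 4.2.
3. **Missing refractive error, OKL eyes on treatment:** use the same eye's nearest measured value in the same treatment state.
4. **Missing corneal radius, either arm:** likewise use the same eye's nearest measured radius in the same treatment state.

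The existing rule for the non-functioning case can stay as it is. Keep the counts, reported by arm and visit.

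In SAP 6.3, add one sensitivity analysis: repeat the key secondary analysis with every affected SFCT value left missing and handled by the mixed model under MAR, in line with 6.4.

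The cost is a few lines of SAP wording, recomputation of the affected choroid values and one extra model run. No new data are needed.
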